### 11 CIP administration

The Principal Investigator has a legal responsibility to the regulatory authorities to fully report all the results of sponsored clinical studies. No investigative procedures other than those stated in this CIP shall be undertaken on the enrolled clinical investigation subjects without the agreement of the IRB and PI.

### 11.1 Amendments

Amendments to the CIP can be made by the investigator and will be communicated to Medela AG. All changes must be documented in a signed CIP amendment. All amendments must be submitted to the IRB for approval prior to implementation.

### 11.2 Deviations

Any deviation from the CIP shall be recorded together with an explanation for the deviation. Medela shall be informed about deviations. Investigator is responsible for analysing them and assessing their significance.

Significant deviations defined as compromising or potentially compromising the safety of the patients, enrollment of non-eligible patients and any deviation which compromises

significantly the outcomes of the study, shall be subject to reporting by Investigator to the IRB within the appropriate deadlines indicated by the IRB.

Note: Where relevant, Competent Authorities should be informed.

# 11.3 Study termination

Medela AG will be allowed to monitor the progression of the clinical investigation. Medela and the Institution shall jointly agree on the scope and plan of the monitoring. If warranted, the clinical investigation may be suspended or discontinued by Investigator early if there is an observation of serious adverse reactions presenting an unreasonable risk to the clinical investigation.

In the event of clinical investigation termination or suspension, Investigator will send a report outlining the circumstances to the IRB, and all I investigators. A suspended or terminated clinical investigation may not be re-initiated without approval of the reviewing IRB.

# 12 Safety

NPWT is currently used in clinical obstetric practice. Further, the adverse events reported with the use of prophylactic NPTW at cesarean were minor. Therefore, no serious or life-threatening adverse events are expected in this trial. Nonetheless, the following measures will be taken to monitor and investigate adverse events.

# 12.1 Adverse Event Reporting

During the course of this clinical investigation adverse events might occur. For the purposes of this study the following categories of adverse events are relevant for reporting:

- Adverse Event of Special Interest (AESI)
- Serious Adverse Event (SAE)
- Adverse Device Effect (ADE)
- Serious Adverse Device Effect (SADE)

Subjects will be evaluated for adverse events in the following manner:

- Routine monitoring by physicians, nurses and research team during inpatient stay, with data obtained from the subject's EMR by research staff.
- Patients will be scheduled for standard of care follow-up with their provider at 1-2 weeks and 4-6 weeks postpartum. Research staff will review the subject's EMR after 6 weeks postpartum.
- Medical records will be sought for any patient or provider-reported complications.

# 12.2 Adverse Events of Special Interest (AESI)

For this study, abnormal laboratory findings (e.g., clinical chemistry, hematology) or other abnormal assessments (e.g., electrocardiogram, X-rays, vital signs) per se are not reported

as AEs. Only Adverse Events of Special Interest (AESI) defined below will be recorded on the CRFs and in the subject's chart.

For this study, AESIs refer to:

- Mild/moderate reactions:
  - o Skin blisters
  - o Wound bleeding
  - Allergic skin reaction

Any current condition that is recorded as a pre-existing condition in the medical history, unless there is a change in nature, severity, or degree of incidence, is not an AE.

Relation to the clinical investigation device will be assessed by help of the following criteria:

- Related
- Not related

Relation to the procedure will be assessed by help of the following criteria:

- Related
- Not related

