# 7 Risk analysis

# 7.1 Risks

The Single Use Prophylactic Negative Pressure Wound Therapy System received FDA marketing approval in 2012. As of September 2015, we identified two reports on the FDA website of blistering at the site of application from the PICO device. A third report of a minor burn from the PICO pump device occurred in a patient after neurosurgery while still unconscious. The patient was found to have been lying on the pump device for a prolonged period of time. Case series suggest approximately 10-15% rate of skin irritation and blisters at the device application site. The majority (~90%) did not require treatment beyond removal of the device. Moreover, adverse events noted with NPWT after cesarean were minor and comparable in frequency to standard dressing.

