# 8.4 Risks to assess

<10% device related adverse events including skin blistering, allergic reaction and wound bleeding.

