# 8.6.1 Secondary endpoints

Efficacy outcome

• Composite wound complication including wound infection, would separation, seroma, antibiotics prescribed for presumed SSI within 30 days (+/- 2 days)

Safety outcomes:

• Skin blistering, allergic reaction, wound bleeding

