### 12.4 Adverse Device Effects (ADE) & Serious Adverse Device Effects (SADE)

An adverse device effect is an adverse event related to the use of a study medical device

This definition includes adverse events resulting from insufficient or inadequate instructions for use, deployment, implantation, installation, or operation, or any malfunction of the investigational medical device.

This definition also includes any event resulting from user error or from intentional misuse of the investigational medical device.

An ADE is classified as serious if it has resulted in any of the consequence characteristics of a serious adverse event or that might have led to any of these consequences if suitable action had not been taken or intervention had not been made or if circumstances had been less opportune.

If an ADE or SADE has occurred any retrievable part of the Invia® Motion™ Endure NPWT system should be returned to Medela AG for analysis. If there is also a suspected relation to accessory material (guide wire etc.) the accessory material in question should also be sent to Medela AG for analysis.

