# Severity of Reportable Events:

The investigator will assess the severity of the AE using the following general guidelines:

| Severity          | Description  |
|-------------------|--|
| Mild:             | An AE that is usually transient, requiring no special treatment, and does not interfere with the subject's daily activities.   |
| Moderate:         | An AE that introduces a low level of inconvenience or concern to
the subject and may interfere with daily activities but is usually
ameliorated by simple therapeutic measures.      |
| Severe:           | An AE that interrupts a subject's usually daily activity and typically requires systemic drug therapy or other treatment (a severe AE may not necessarily qualify as an SAE).              |
| Life-threatening: | An AE that put the subject at immediate risk of death from the event as it occurred. This does not include an event that might have led to death if it had occurred with greater severity. |

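### Section 12.2 limits CRF recording to mild or moderate reactions, contradicting the safety endpoint and the other adverse-event sections, and leaves one class of endpoint event with no reporting category

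*Combined protocol and SAP*

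**What the plan says.** Section 12.2 restricts what is recorded: "Only Adverse Events of Special Interest (AESI) defined below will be recorded on the CRFs and in the subject's chart". The definition that follows is headed "Mild/moderate reactions" and lists skin blisters, wound bleeding and allergic skin reaction.

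Other sections are wider:

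- **8.6.1** gives the safety outcomes as "Skin blistering, allergic reaction, wound bleeding", with no limit on severity or on relation to the device.
- **8.4** sets the risk to assess as "<10% device related adverse events including skin blistering, allergic reaction and wound bleeding". It is confined to device-related events, has no severity limit, and its list is open-ended.
- **12.1** makes SAEs, ADEs and SADEs relevant for reporting alongside AESIs.
- **12.4** defines the ADE without reference to severity: "An adverse device effect is an adverse event related to the use of a study medical device".
- **12.5** requires a report for each event, graded from mild up to death. Its timeline for AESIs that are not severe presupposes that some are. Its severity table adds that "a severe AE may not necessarily qualify as an SAE".
- **13** requires all four categories in the subject's source record, with severity, and says that study data are then entered in the eCRFs.
- **10.5.2** schedules an AE/SAE form at all three contacts after enrollment.

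**The concern.** The recording rule is narrower than the endpoint it feeds. If a site follows 12.2 as written, the CRF holds the milder blisters, bleeds and allergic reactions and lacks the severe ones, which matter most to a safety summary. If it follows 12.1, 12.5 and 13, it records more. Two sites could reasonably choose differently, and section 15 plans subgroup analyses by site, so a difference in recording practice could appear as a difference in safety.

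The direction of any error is fixed: leaving events out can only lower the reported proportion. In a study of 30 women, one patient more or less changes the result visibly.

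**Working it through.** The documents give no calculation to reproduce. The 10% in 8.4 has no derivation, and 15.1 sets 30 patients without a formal estimate. The check is therefore mainly a comparison of sections.

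**Step 1. Trace each class of event through the rules.** The first five rows concern a blister, bleed or allergic reaction.

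| Event | In 8.6.1 endpoint | In 8.4 target | AESI under 12.2 | Other category | Result |
|---|---|---|---|---|---|
| Mild or moderate, device-related | Yes | Yes | Yes | ADE | Recorded |
| Mild or moderate, not device-related | Yes | No | Yes | None needed | Recorded |
| Severe and serious | Yes | If device-related | No | SAE, or SADE if related | Rules conflict |
| Severe, non-serious, device-related | Yes | Yes | No | ADE | Rules conflict |
| Severe, non-serious, not device-related | Yes | No | No | None | Gap |
| Skin irritation, device-related | Not named | Yes, as the list is open | No | ADE | Rules conflict |

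The fifth row is possible on the protocol's own terms, because the severity table in 12.5 separates severe from serious.

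**Step 2. Weight of one patient.** With n = 30 (15.1), all analysed:

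- 1/30 = 3.3 percentage points.
- 2/30 = 6.7%, exact (Clopper-Pearson) 95% interval 0.8% to 22.1%.
- 3/30 = 10.0%, interval 2.1% to 26.5%.

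An observed rate below 10% therefore means at most 2 patients, and one unrecorded patient separates 6.7% from 10.0%. The intervals overlap almost entirely.

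**Step 3. Illustration for severe events, under stated assumptions.** Section 7.1 says: "Case series suggest approximately 10-15% rate of skin irritation and blisters at the device application site". It adds that about 90% needed nothing beyond removal of the device. Assume that this background rate applies here, and that the other 10% or so stand in roughly for severe events. Neither assumption is in the plan.

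- Expected patients lost: 30 × 0.10 × 0.10 = 0.30, up to 30 × 0.15 × 0.10 = 0.45.
- P(at most 2 of 30), binomial, at a true rate of 10%: 0.41 with all events counted. With the counted rate at 0.10 × 0.9 = 9%, it is 0.49.
- At a true rate of 15%: 0.15 with all events counted. With the counted rate at 0.15 × 0.9 = 13.5%, it is 0.21.

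On this stand-in, the chance of observing a rate below 10% rises by 0.06 to 0.08.

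**Step 4. Skin irritation.** Section 7.1 pools irritation with blisters and gives no split. If irritation-only events made up 25%, 50% or 75% of the total (assumed) and all went uncounted, the same probability would be 0.61, 0.81 or 0.96 at a true 10%, and 0.33, 0.61 or 0.90 at a true 15%. The spread shows that the result depends on a share the documents do not supply.

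**The case against.** The strongest reply is that 12.2 is badly drafted but harmless. The restrictive sentence directly follows one that excludes isolated laboratory and assessment findings, so its likely purpose is to avoid collecting routine events. Read literally it would also bar SAEs, which cannot be intended given 10.5.2 and 13. Severe device-related events are ADEs and serious events are SAEs, so both are reportable with a grade. Daily inpatient monitoring (10.4), the outcome forms (10.2), chart abstraction through 6 weeks (10.5.1) and record review (12.1) give further routes to an event.

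Most of this stands. It does not remove the contradiction, because the restrictive sentence names both the CRFs and the chart and nothing says which section prevails. Nor does it supply a category for a severe, non-serious event judged not device-related. Chart review may find such an event, but no adverse-event rule requires it to be reported.

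Stronger readings that a reader might infer, and why they fail:

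- **That severe events are left out of the safety results.** The documents support conflicting rules, with omission as the outcome of one reading.
- **That the gap biases the 8.4 target.** The one class without a category is not device-related, so it cannot enter that numerator.
- **That under-recording turns a failed criterion into a met one.** Section 8.4 lists a risk to assess with no pass/fail rule, and section 15 plans only proportions with 95% confidence intervals.
- **That skin irritation is missing from the endpoint.** Section 8.6.1 never included it, and no comparison with the background rate in 7.1 is planned. Adding it would be a preference.

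**Conclusion.** The point holds as an internal contradiction with one real gap. Section 12.2 conflicts with 8.4, 8.6.1, 12.1, 12.4, 12.5 and 13 on which events reach the CRF. For serious events and for device-related events, the defect is that two recording rules compete. For a severe, non-serious blister, bleed or allergic reaction judged not device-related, no reporting category exists although the event belongs to the safety endpoint.

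If 12.2 is followed literally, the error can only be downward, at 3.3 percentage points per patient omitted out of 30. How many patients that would be is unknown, since the documents give neither the severe share nor the irritation share. The figures in steps 3 and 4 are illustrations under assumed shares, and no size of bias is established.

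**What to change.** Change 12.2 in two places and add one reporting line:

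1. Delete the mild/moderate qualifier, so that AESIs are skin blisters, wound bleeding and allergic skin reaction at any severity. This closes the gap for severe, non-serious, unrelated events.
2. Replace the restrictive sentence with: *AESI of any severity and all SAE, ADE and SADE will be recorded on the CRFs.* This agrees with 12.1 and 13, and 13 already covers the source record.
3. In section 15, state that the safety endpoint is reported by severity, using the grade collected under 12.5.

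Device-related skin irritation is then captured as an ADE and counts under the open-ended wording of 8.4. The 8.6.1 endpoint need not change.

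The cost is a short signed amendment with IRB approval (11.1) and a check that the CRF accepts these categories and grades. No visit is added. The reported event rate may be slightly higher. The change is best made before enrollment, since events not recorded at the time may be hard to recover.

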# 12.3 Serious Adverse Events (SAE)

A serious adverse event (SAE) is any adverse event that results in any of the following outcomes:

- Maternal death
- Serious deterioration in the health of the subject, that either resulted in
  - 1) A life-threatening illness or injury, or
    - 2) A permanent impairment of a body structure or a body function, or
  - 3) In-patient or prolonged hospitalization, or
  - 4) Medical or surgical intervention to prevent life-threatening illness or
  - 5) Injury or permanent impairment to a body structure or a body function

Planned hospitalization for a pre-existing condition, or a procedure required by the CIP, without serious deterioration in health, is not considered a serious adverse event.

This also applies to adverse events that may not be immediately life-threatening or result in death or hospitalization but may jeopardize the subject or may require intervention to prevent one of the other outcomes listed above.

The assessment of 'seriousness' is independent from any relation to the investigational device.

Hospitalization is defined by a medical need for in-patient hospitalization overnight. For procedures that are commonly performed in out-patient clinic but yet requires hospitalization solely based on non-medical needs (e.g. logistical reasons) this criterion could be considered

not applicable by the Investigator. Proper documentation of the reasons for decision is required in this case.

Events that are planned (e.g. elective surgery) and documented prior to clinical investigation entry will not be recorded if the procedure is performed without any complications. Medication received during this activity may be recorded.

### 12.4 Adverse Device Effects (ADE) & Serious Adverse Device Effects (SADE)

An adverse device effect is an adverse event related to the use of a study medical device

This definition includes adverse events resulting from insufficient or inadequate instructions for use, deployment, implantation, installation, or operation, or any malfunction of the investigational medical device.

This definition also includes any event resulting from user error or from intentional misuse of the investigational medical device.

An ADE is classified as serious if it has resulted in any of the consequence characteristics of a serious adverse event or that might have led to any of these consequences if suitable action had not been taken or intervention had not been made or if circumstances had been less opportune.

If an ADE or SADE has occurred any retrievable part of the Invia® Motion™ Endure NPWT system should be returned to Medela AG for analysis. If there is also a suspected relation to accessory material (guide wire etc.) the accessory material in question should also be sent to Medela AG for analysis.

### 12.5 Reporting Adverse Events

An adverse event report will be generated for each event that will include the following:

- Date of event discovery
- Severity (mild, moderate, severe, life threatening/disabling, death)
- Relationship to treatment
- Action taken
- Outcome
- Expected or unexpected
- Date reported
- Relevant notes/chart records/supporting documentation to corroborate the event
- To whom event was reported (IRB, Sponsor)
  - Non-Severe AESIs and ADEs will be reported to the Sponsor every 6 months, and to the IRB at renewal.
  - SAEs and USADEs will be reported within 24 hours of discovery to the IRB and the Sponsor.

# Relationship of Reportable Events:

An Investigator must make the determination of relationship to the drug for each AESI/ADE. The relationship to the device should be assessed using the guidelines presented in the table below.

| Relationship to
Device | Description  |
|---------------------------|--|
| Related                   | 
 
Previously known harmfulness of device; or
 
Follows a reasonable temporal sequence from administration of the device; or
 
 |

|           |   |
|------------------|---|
|                  | 
 
Follows a known or expected response pattern to the suspected
 
   |
|                  | intervention; or  |
|                  | 
 
Is confirmed by stopping or discontinuing the device; and
 
   |
|                  | 
 
That is not explained by any other reasonable hypothesis
 
  |
| Probably related | 
 
Follows a reasonable temporal sequence from the time of study
 
   |
|                  | intervention; and/or   |
|                  | 
 
Follows a known response pattern to the study device; and
 
   |
|                  | 
 
Was unlikely to have been produced by other factors such as the
 
   |
|                  | subject's clinical state, therapeutic intervention, or concomitant therapy  |
| Possibly related | 
 
Follows a reasonable temporal sequence from the time of study
 
   |
|                  | intervention; and/or   |
|                  | 
 
Follows a known response pattern to the study device; but
 
   |
|                  | 
 
Could have been produced by other factors such as the subject's
 
   |
|                  | clinical state, therapeutic intervention, or concomitant therapy  |
| Unlikely related | • Does not follow a reasonable temporal sequence from the time of study   |
|                  | intervention; and
• Was likely produced by other factors such as the subject's clinical state  |
|                  | 
 
Was likely produced by other factors such as the subject's clinical state,
therapeutic intervention, or concomitant therapy but for which
 
 |
|                  | relationship cannot be definitely ruled out   |
|                  |   |
| Not related      | The adverse event can be determined with certainty to have no   |
|                  | relationship to the study device  |

# Severity of Reportable Events:

The investigator will assess the severity of the AE using the following general guidelines:

| Severity          | Description  |
|-------------------|--|
| Mild:             | An AE that is usually transient, requiring no special treatment, and does not interfere with the subject's daily activities.   |
| Moderate:         | An AE that introduces a low level of inconvenience or concern to
the subject and may interfere with daily activities but is usually
ameliorated by simple therapeutic measures.      |
| Severe:           | An AE that interrupts a subject's usually daily activity and typically requires systemic drug therapy or other treatment (a severe AE may not necessarily qualify as an SAE).              |
| Life-threatening: | An AE that put the subject at immediate risk of death from the event as it occurred. This does not include an event that might have led to death if it had occurred with greater severity. |

# Outcomes of Reportable Events:

The investigator will categorize the outcome of each reportable event according to the definitions below:

| Status                  | Description   |
|-------------------------|---|
| Resolved:               | The subject recovered from the SAE or AESI.   |
| Resolved with sequelae: | A condition whereby the consequences of a disease or injury include lingering effects.  |
| Ongoing:                | At the time of the last assessment, the event is ongoing, with an
undetermined outcome. Note: Ongoing SAEs and AESIs are not
considered resolved as a result of death and no SAE or AESI
stop date should be recorded for an AESI that is ongoing at the
time of death. |
| Fatal:                  | Adverse Event directly caused death. If a subject dies during participation in the study the lead site should be provided with a copy of any post-mortem findings. Note: Death is an outcome of   |

| an adverse event and not an adverse event in itself. All reports of subject death should include an adverse event term (other than |
|--|
| "Death") for the cause of the death.   |

### 13 Data management

Qualified study staff at the investigational site will perform primary data collection. Paper source will be used to collect all subject data during the study. All study data will then be entered into REDCap in electronic case report forms (eCRFs). The investigator is responsible for the accuracy and completeness of all data on the eCRFs. Site personnel will review completed eCRFs at regular intervals throughout the study.

Information on the eCRFs will be compared for completeness, validity, and consistency to information originally recorded on source documents related to the study. Information on the eCRF must match the same information on the source documents or a data query will be issued.

The PI/data manager is responsible for providing a clean data set at the end of the clinical investigation. Queries should be resolved by the investigator or a person designated by the investigator in a timely manner. When all data is complete the database will be locked and the data analyzed.

Quality control audits of all key performance and safety data in the database will be made after 90% of all data have been entered and processed. Prior to database lock, the entire database will be re-validated to ensure that there are no outstanding errors. When all queries have been resolved, the database will be locked. Any changes to the database after that time will require joint written agreement between the PI and Sponsor.

The Investigator is responsible for reporting appropriately and in a legible manner the requested information in the CRFs.

The medical/ subject record (source document) must contain but is not limited to the following information:

- Date of informed consent
- Subject participation in the clinical investigation
- Demographics
- Dated reports of the discharge
- Documentation of medical/ surgical history and current medication
- Description of device procedure (material used, date, time, complications etc.)
- All AESI, SAE, ADE, or SADEs: Diagnosis and symptom(s), onset and end date, severity, action taken, outcome
- Concomitant medication
- Date of clinical investigation completion or withdrawal

